9.1 Screening Evaluations

There will be three primary components to the screening process: the chart review in the acute care setting (phase 1), the phase 2 screen, and screening for final eligibility (phase 3) that includes the 3MS and the SMWT. These components will be typically administered over three contacts. Those who qualify after phases 1 and 2 will be invited for the first study visit for phase 3 screening.

9.1.1 Modified Mini-Mental State Examination (3MS)

The 3MS is a test of global cognitive function which assesses a broad variety of cognitive dimensions and is an expanded 100 point version of the original Folstein Mini-Mental State Exam.^{137,138} The 3MS will be used at the baseline visit to identify and exclude participants with cognitive impairment (3MS score <73).¹³⁹

9.2 Primary Outcome Measure: Community Ambulation

The Six-Minute Walk Test (SMWT) will be used to obtain a continuous measure of total distance walked in six minutes. The SMWT is highly correlated with workloads, heart rate, oxygen saturation, and dyspnea responses when compared to bicycle ergometry and treadmill exercise tests in older persons. It has been performed by elderly, frail and severely compromised participants who cannot perform standard maximal treadmill or cycle ergometry exercise tests. Performance of the SMWT at the baseline assessment also will be used to define final eligibility prior to the collection of additional baseline data. Participants who walk less than four meters in 40 seconds (<0.1 m/sec) or who walk 300 meters or more in six minutes will be excluded from the trial. Participants with angina, extreme shortness of breath, or ambulating with severe pain during the SMWT also will be excluded.

Participants will be asked to walk back and forth on a measured path marked clearly at both ends for turning purposes, while being told when each minute has passed, and receiving verbal encouragement ("you're doing well" or "keep up the good work") every 60 seconds. Test-retest reliability in older adults is excellent ($r = .95$).¹¹² Concurrent validity with $V0_2$ peak ($r=.64$) and cycle ergometry ($r=.58$) have been reported.^{110,140,141}

9.3 Secondary Outcome Measures

9.3.1 Cognitive Function (3MS)

The Mini Mental Status Exam (MMSE) is one of the most widely used screening instruments for dementia. The Modified Mini-Mental State (3MS) test was developed to overcome shortcomings of the MMSE, specifically its narrow range of possible scores and ceiling effects. The 3MS incorporates four additional items (on long-term memory, abstract thinking, category fluency, delayed recall), more uniform administration, and refined scoring, in order to sample a broader variety of cognitive functions, cover a wider range of difficulty levels, and enhance the reliability and validity of the test scores. The 3MS test has a score range of 1-100. It can provide an estimated score of the MMSE, and can also be used to monitor cognitive change over time.

9.3.2 Short Physical Performance Battery (SPPB)

The SPPB evaluates lower extremity performance in older persons based on timed short distance walk, repeated chair stands, and a set of balance tests.¹⁴²⁻¹⁴⁴ Each of the tasks is assigned a score ranging from 0 to 4, with 4 indicating the highest level of performance and 0 an inability to complete the test. The test takes about 10-15 minutes to administer and was designed to be administered by a lay interviewer in a setting with limited space. The battery has

an excellent safety record. It has been administered to well over 10,000 persons in various studies and no serious injuries are known to have occurred. The SPPB components and total score are derived from normative values obtained from a population-based study.^{142,144} The total score ranges from 0 to 12; there are three subscales embedded in the SPPB.

Standing balance. For the test of standing balance, participants are asked to maintain balance in three positions, characterized by a progressive narrowing of the base support: with feet together (side-by-side position), the heel of one foot beside the big toe of the other foot (semi-tandem position), and the heel of one foot in front of and touching the toes of the other foot (tandem position). For each of the three positions, participants are timed to a maximum of 10 seconds.

We will use an enhanced balance measure that includes the balance subscale of the Short Physical Performance Battery (SPPB) and two additional single leg stands (eyes open and eyes closed), as used in the National Health and Aging Trends Study (NHATS).¹⁶⁰ For the test of standing balance, participants are asked to maintain balance in three positions, characterized by a progressive narrowing of the base support: with feet together (side-by-side position), the heel of one foot beside the big toe of the other foot (semi-tandem position), and the heel of one foot in front of and touching the toes of the other foot (tandem position). For each of the three positions, participants are timed to a maximum of 10 seconds. Participants are then asked to stand on one leg (on the side of the fracture) with eyes open and again with eyes closed. Each of the single leg stands are held for up to 30 seconds. The number of seconds is then summed across the 5 items to obtain the measure of balance. These tests are hierarchical such that when a participant fails an item, the harder ones are not administered and receive a score of 0.

Walking speed. Walking speed is assessed by asking participants to walk at their usual pace over a 4 m course. Participants are instructed to stand with both feet touching the starting line and to start walking after a specific verbal command. Participants are allowed to use walking aids (cane, walker, or other walking aid) if necessary, but not the assistance of another person. Timing begins as soon as the participant starts to walk and the time in seconds needed to complete the entire distance is recorded. The faster of two walks is used to compute walking speed.

Chair stands. The repeated chair stands test is performed using a straight-backed chair, which is placed with its back against a wall. Participants are first asked to stand once from a sitting position with their arms folded across their chest. If they are able to perform the task, they are then asked to stand up and sit down five times, as quickly as possible. The time to complete the task is recorded.

9.3.3 Activities of Daily Living (ADLs)

We will measure ADLs using the Pepper Assessment Tool for Disability (PAT-D)^{145,146} with two modifications. First, two items (walking a quarter mile and walking across a small room) were added to address perceived gaps in the original PAT-D scale. This modification is consistent with the version used in the Lifestyle Interventions and Independence for Elders study.¹⁴⁷ Second, two items (walking several blocks and lifting heavy objects) were deleted to avoid duplication with other items in the scale. The resulting 19-item scale allows examination of three subscales (basic ADL, functional limitations, and instrumental ADL).

9.3.4 Quality of Life (SF-36)

We will use an interviewer-administered version of the SF-36, a health survey that assesses quality of life in eight subscales (physical function, social function, role-physical, role-emotional, bodily pain, mental health, general health, and vitality).¹⁴⁸ The measure has been validated as a generic measure of quality of life in many different populations, including patient and non-patient samples.^{148 61,149,150}

9.3.5 Nutritional Status

Nutritional status will be assessed using the Mini Nutritional Assessment-Short Form (MNA®-SF),^{117,151} a validated and widely used malnutrition screening tool.¹⁵¹⁻¹⁵⁴ We are using a modified version of the MNA®, approved by the scale's developer (the Nestlé company), to facilitate use as an interviewer-administered tool in a research setting. Scores range from 0 to 14; participants scoring ≤ 7 will be considered malnourished; those scoring 8-11 will be considered to be at risk of malnutrition; and those scoring 12-14 will be considered to have normal nutritional status.^{117,151}

9.3.6 Muscle and Fat Mass

Lean mass will be estimated using dual-energy x-ray absorptiometry (DXA) (GE LUNAR, Madison, WI). DXA calculates fat and lean tissue mass from the total body scan. The coefficient of variation of these measurements in our previous studies for fat and lean mass was 1.4% and 1.3%, respectively.

9.3.7 Muscle Composition: Intramuscular fat and muscle volume

Thigh CT will be performed every 4 cm starting at the patella and ending at the femoral head (Siemens Somatom Sensation 64 Scanner) to quantify skeletal muscle area, total fat area, low density lean tissue area, and muscle attenuation of the thigh. Scans will be analyzed using MIPAV (Medical Image Processing, Analysis and Visualization, v.7.0, NIH). The cross-sectional area of each axial slice will be multiplied by the distance between slices (4 cm) and summed across slices representing volume expressed in cm³. The average attenuation of muscle tissue and the percentage of low-density lean muscle to total muscle volume is associated with skeletal muscle lipid content, and a measure of muscle quality.

9.3.8 Strength

A BiodeX System 3 PRO dynamometer will measure concentric isokinetic peak normalized joint torque over the entire range of motion (strength) for bilateral ankle plantarflexion-dorsiflexion and knee flexion-extension. Strength is measured in Newton-meters (Nm). Testing will utilize standardized positioning and joint motion excursions. Subjects will perform two blocks of three repetitions with a rest period between blocks.

9.3.9 Power

A BiodeX System 3 PRO dynamometer will measure strength per unit of time (power) for bilateral ankle plantarflexion-dorsiflexion and knee flexion-extension. Power is measured in Watts (W). Testing will utilize standardized positioning and joint motion excursions. Subjects will perform two blocks of three repetitions with a rest period between blocks.

9.3.10 Bone Mineral Density

BMD will be estimated using DXA as described above. DXA of the contralateral (non-fractured) femur will be measured to yield measures of total hip and femoral neck BMD.

9.3.11 Gait and Balance (GAITrite)

A GAITrite instrumented walkway system will measure spatial and temporal gait parameters. Subjects will walk at their safest fast and natural speeds. In addition, the Dynamic Gait Index, a clinical assessment of balance and mobility while walking, will be administered. Measures will include: step length, walking speed, single and double leg support time, and cadence.

9.3.12 Bone Turnover Markers

Bone turnover markers. a) bone formation (serum aminoterminal propeptide of type 1 procollagen; P1NP) and b) bone resorption (serum cross-linked C-telopeptides of type I collagen; CTx-I) will be assessed.

9.3.13 Hormones

Parathyroid hormone, intact (iPTH) will be measured by ELISA.

9.3.14 Inflammatory Cytokines

a) interleukin-6 (IL-6), b) soluble TNF- α receptor 1 (sTNF- α R1), c) IL-1 receptor antagonist (IL-1ra), and d) interleukin-10 (IL-10). All cytokines will be measured in serum by ELISA (R&D Systems Inc., Minneapolis, MN).

9.3.15 Cognitive Function (Trail Making Test (Trails A and B))

The Trail Making Test is a neuropsychological test of visual attention and task switching. It consists of two parts in which the subject is instructed to connect a set of 25 dots as quickly as possible while still maintaining accuracy. The test can provide information about visual search speed, scanning, speed of processing, mental flexibility, as well as executive functioning. It is sensitive to detecting cognitive impairment associated with dementia.

9.3.16 Waist Circumference

Waist circumference (cm) reflects adipose tissue distribution and is believed to be influenced by glucocorticoid activity. Waist measurement will be taken by measuring tape of the waist circumference (narrowest section between the ribs and iliac crest). Waist circumference will be measured in centimeters.

9.4 Improvement in Walking

Whether or not there was an increase of at least 50 meters in the distance walked on the SMWT will be assessed as a tertiary outcome. This distance has been shown to be clinically meaningful.^{142,160}

9.5 Clinical and Background Characteristics

Information on a small number of other patient characteristics will be collected to allow description of the study population, to allow analyses of differential effects in subgroups (i.e., effect modification), and to help in the interpretation of results.

9.5.1 Demographic and Surgical Characteristics

For descriptive purposes, information on the following participant characteristics will be collected either during screening or at the baseline assessment: age, gender, race, living situation, marital status, educational level, fracture type, and surgery type.

9.5.2 Functional Comorbidity Index

The Functional Comorbidity Index (FCI) is a clinically based measure developed by Groll *et al.* This index includes a checklist of 18 comorbid conditions scored 1 or 0. A maximum score of 18

indicates the highest number of comorbid illnesses. The FCI was specifically developed to predict physical functioning.¹⁶¹

9.5.3 Weight, Height, and BMI

Height (in feet and inches) will be measured once at the baseline visit using a standard stadiometer. Weight (in pounds) will be measured using a digital scale at baseline and follow-up visit. Measured height and weight will be used to calculate BMI.

9.6 Other Measures to be Monitored

9.6.1 Adherence

Adherence with PUSH intervention. PTs will submit a visit form for each of the 32 visits that records date of visit; start and end time of the visit; reason for missed visit; what activities were performed; and whether activities were performed as prescribed. We will also obtain information about the intensity of each activity at initiation of the intervention and every four weeks during the intervention period. Logs completed by PTs will record the detail of each designated activity during intervention sessions as well as any precautions or modifications to activities. Reasons for protocol variations will be noted in the PT log books.

Adherence with protein supplement. We will monitor adherence to the protein supplement by weighing the container(s) of protein powder every 4 weeks during the 16-week intervention period and by self-report during the 4-week telephone calls.

Adherence with study vitamins/supplements. Vitamin D, calcium, and multivitamin adherence will be monitored by pill counts every four weeks during the intervention period and by self-report during the 4-week telephone calls for the entire 16-week study period.

9.6.2 Weight Loss

Weight will be monitored by the PTs every four weeks during the 16-week intervention period using a standard digital scale.

9.6.3 Reportable Adverse Events (RAEs)

Reportable adverse events (RAEs), which include serious adverse events (SAEs), unexpected AEs or injury that occurs under supervision by study staff, will also be obtained during the study. Participants will be screened for possible RAEs every four weeks during the telephone interviews using standardized questions. Participants (or their proxies) will be asked about life-threatening or significant medical events and the outcomes of these events. RAEs will also be asked about by study staff prior to each PT visit and clinical site follow-up assessment. RAEs may be spontaneously reported to any study staff member throughout the study (see section 12.4.1).

9.6.4 Expected Adverse Events (AEs)

Expected AEs will be assessed every four weeks during the telephone interview. Participants (or their proxies) will be asked a series of standardized questions related to pain (feet, hip, back, knees, digestive and stomach); breathing problems or chest pain; bloating or puffiness in legs, ankles, or feet; drowsiness, dizziness, or confusion; shakiness, anxiety, clammy skin, or irritability; and falls (with and without injury).

Section 10: Study Procedures

10.1 Baseline Assessments

The baseline assessments will be performed immediately following screening for phase 3 criteria.

Certain components of the baseline assessment are required by all participants in the pilot study in order to make useful comparisons to data from participants in CAP and CAP-MP and to have enough power to achieve primary and secondary research aims. Other assessments at the baseline visit will allow comparisons for other outcome measures. Participants who perform the required components (marked with a pound sign (#) in the list below) will be eligible to receive the PUSH Plus Protein intervention. All baseline data collection must be completed within 14 days of the SMWT.

The items with an asterisk (*) are collected as part of phase 3 screening:

- Baseline Anthropometry #
- Demographics and Blood Draw Information # *
- Modified Mini-Mental State Examination # *
- Six-Minute Walk Test # *
- Baseline Interview #
- Short Physical Performance Battery #
- SF-36 Health Survey #
- Pepper Assessment Tool for Disability #
- Mini Nutritional Assessment-Short Form #
- Trail Making Test (Trails A and B)
- Blood draw (for serologic and genetic tests)
- Reportable Adverse Events
- CT scan of thigh #
- DXA scan of whole body #
- DXA scan of hip
- GAITrite
- Four-Square Step Test
- Bidex strength testing (knee flexion/extension)

10.2 Follow-up Assessment

The following measures will be obtained at 16 weeks after baseline testing.

- Reportable Adverse Events
- Six-Minute Walk Test
- Modified Mini-Mental State Examination
- Short Physical Performance Battery
- SF-36 Health Survey
- Weight and waist circumference
- Pepper Assessment Tool for Disability
- Mini Nutritional Assessment-Short Form
- Trail Making Test (Trails A and B)
- Blood draw (for serologic and genetic tests)
- CT scan of thigh
- DXA scans of hip and whole body
- GAITrite

- Four-Square Step Test
- Biodex strength testing (knee flexion/extension)

10.3 Telephone Interviews

Structured telephone interviews will be conducted every four weeks for 16 weeks starting four weeks after the last date of baseline testing. The following measures will be administered:

- Reportable Adverse Events (RAE) Form
- Expected Adverse Events (AE) Form
- Self-reported adherence to protein and supplements

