10.4 Timing of Study Procedures

The target date for completion of the pre-baseline testing (i.e., screening) assessments will be anchored to the date of admission to the hospital for hip fracture. The target date for completion of all other assessments will be anchored to the date on which all baseline testing is completed (see Table 1).

Note: In cases where the participant performs all required baseline measures and then performs additional baseline measures, the date on which baseline testing is completed is defined as the date on which the participant performed the last assessment within the allowable window for baseline testing (up to 26 week post hospital admission). In cases where additional baseline measures have been scheduled but cannot be completed within the allowable window for baseline testing, (e.g., scheduling conflict, not safe), the date on which baseline testing completed is defined as the date on which staff establishes definitively that no additional baseline measures can or will be attempted.

Table 1. Timing of Study Procedures

PROCEDURE	TARGET DATE	ALLOWABLE INTERVAL
Phase 3 screening	As early as possible following admission	Up to 26 weeks post-admission
Baseline assessment	As early as possible following admission	Up to 26 weeks post-admission
Dietitian consult	1 week after baseline testing is completed	+1 week
First intervention visit	1 week after baseline testing is completed	+16 weeks
First telephone interview	4 weeks after baseline testing is completed	-1 week, +3 weeks
Subsequent telephone interviews	At 4-week intervals from date on which baseline testing is completed	-1 week, +3 weeks
First follow-up assessment	16 weeks after baseline testing is completed	+2 weeks
Out-of-window assessment	16 weeks after baseline testing is completed	0-16 weeks and 18-38 weeks after baseline testing is completed

At baseline, all participants will, by design, be tested at the clinical site. At the follow-up visit, we will attempt to test all participants at the clinical site. When this is not possible, we will attempt to have study staff administer the test in a non-study clinical facility or, failing that, at another non-study location or the participant's home.

Section 11: Safety Assessments

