12.5 Expected AE and RAE Collection and Reporting

The requirements for reporting RAEs will begin when the participant provides informed consent and will end 30 days after the participant's involvement in the study has ended. Expected AEs will be assessed every four weeks after baseline testing. Figures 5a-d provide algorithms describing the reporting process.

Figure 5a. Collection and Reporting Process for Expected AEs

[figure not shown]

Figure 5b. Collection and Reporting Process for RAEs Collected during Standardized Telephone Interviews

[figure not shown]

Figure 5c. Collection and Reporting Process for RAEs Identified Anytime Other than During a Standardized Telephone Interview

[figure not shown]
[figure not shown]

Figure 5d. Review and Reporting Process for RAEs

Timeline for Reporting Events

The RAE reporting schedule is shown below:

1. Staff will report RAEs to the PI and study physician as soon as the event is known and submit documentation of the event to the study coordinator in real time.
2. All injuries that occur while a participant is under the supervision of study personnel and all participant deaths (regardless of relatedness) will be reported to the OAIC Program Director within 24 business hours (excluding weekends and holidays) of the PI becoming aware of the event.
3. Events that are reviewed by the ISM and subsequently classified as related or possibly related to the research will also be submitted to the OAIC Program Director.
4. All other RAEs, SAEs, expected AEs, and protocol deviations will be requested semiannually by the OAIC to be presented to the DSMB.

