12.8 Reporting Expected AEs and RAEs to the UM-OAIC DSMB

The UM-OAIC DSMB will review tabulated data on non-serious and expected AEs on a semi-annual basis and monitor for adverse event rates out of proportion to those expected. The PI (or designee) will forward the individual Reportable Adverse Event Record and AE Narrative for each event requiring immediate notification to the UM-OAIC DSMB and NIA as well as a table showing all RAEs to the UM-OAIC DSMB and NIA semi-annually. The UM-OAIC DSMB will review all RAEs that are temporally related to the intervention in aggregate form at its scheduled meetings.

All RAEs that relate to hazards of the study intervention or are cause for urgent concern will be reported to the UM-OAIC DSMB chair, NIA, and the UMB IRB immediately after recognition of their importance. The DSMB chair may conclude that an RAE is of universal and immediate concern. The DSMB chair may also recommend convening the UM-OAIC DSMB to review participant safety based on any individual report or accumulating evidence.

Section 13: Intervention Discontinuation

Certain RAEs may result in a temporary interruption or early discontinuation of the trial assessments and interventions or components of these assessments and interventions. Please refer to the appropriate MOP chapter(s) for specific instructions on stopping criteria during screening, intervention, and follow-up assessments.

After such RAEs occur, a participant may resume the trial intervention when the study physician and the primary care provider (if participant has one) agree that it is appropriate. For mild problems that require temporary cessation of intervention, the PI, in consultation with the study physician and participant, may agree to reintroduce the participant to the study intervention.

At any time, the UM-OAIC DSMB may recommend discontinuation of any component or intervention group of the study for any of the following reasons:

- 1) Compelling evidence from this or any other study of an adverse effect of the study intervention(s) that is sufficient to override any potential benefit of the interventions to the target population.
- 2) Compelling evidence from this or any other study of a significant beneficial effect of the study intervention(s), such that its continued denial to other study group(s) would be unethical.
- 3) A very low probability of addressing the study goals within a feasible time frame.

Section 14: Data Analyses

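### The Expected AE Form is not given at baseline or at the 16-week visit, so in this single-arm study its counts cannot reliably be read as treatment-emergent

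*Protocol*

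**What the plan says.** Protocol 10.3 sets the calls: "Structured telephone interviews will be conducted every four weeks for 16 weeks starting four weeks after the last date of baseline testing". The "Expected Adverse Events (AE) Form" is one of the three items given in them. Two other sections agree on mode and start. Section 9.6.4 says "Expected AEs will be assessed every four weeks during the telephone interview", and 12.5 says "Expected AEs will be assessed every four weeks after baseline testing". Table 1 in 10.4 puts the later calls "At 4-week intervals from date on which baseline testing is completed", with the same window of one week early to three weeks late as the first call.

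The clinic visits are different. The baseline list in 10.1 and the list in 10.2, introduced by "The following measures will be obtained at 16 weeks after baseline testing", each contain Reportable Adverse Events but not the Expected AE Form.

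Two uses depend on the expected-AE data. Section 4.2 makes safety and tolerability a study objective, and under 12.8 the DSMB is to "monitor for adverse event rates out of proportion to those expected".

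**The concern.** Section 12.3 lists pain at several sites, leg swelling, dizziness and falls among the expected events. People recovering from a hip fracture can have these before any study treatment. Section 5.1 itself reports that 53% of patients who lived in the community before fracture fell at least once in the following six months. That is a background rate and not a prevalence at entry, but it shows how much of what the form records can arise without the intervention.

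All participants receive PUSH Plus Protein, so no concurrent group shows the background level. Without a starting value on the same items, a report of hip pain at week 4 may be persistence, worsening or a new problem. The safety objective and the DSMB's comparison with expectation both need those separated. Section 12.2.2 also treats an expected event as unexpected, and hence reportable, when its frequency or severity goes beyond what was anticipated. That judgement is weakly supported without a starting point.

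**Working it through.** **Where each kind of event is recorded**

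| Occasion | Expected AE Form | Reportable AEs |
|---|---|---|
| Baseline visit (10.1) | not listed | listed |
| Calls, target weeks 4, 8, 12, 16 (10.3) | listed | listed |
| 16-week visit (10.2) | not listed | listed |

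The right-hand column does not stand in for the left. Section 12.4 defines reportable events as serious events, unexpected events and injuries under study supervision. Section 12.4.2 defines unexpected events as ones not listed in the consent form or in 12.3. Non-serious hip pain, knee pain, swelling or dizziness therefore falls outside the reportable category unless it is more frequent or severe than anticipated.

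**What is known before treatment**

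- SF-36 bodily pain is collected at baseline (9.3.4, 10.1), but not by body site.
- Chest pain or shortness of breath, and walking with severe pain in the baseline six-minute walk, are exclusions (7.3, items 6.5 and 6.9). Lesser hip pain is not.
- A Baseline Interview is required (10.1), but its content is not described.

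**Call dates** (Day 0 = last day of baseline testing)

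- Target of call k: 28k days, which gives Days 28, 56, 84 and 112.
- Window: 28k − 7 to 28k + 21, which gives Days 21–49, 49–77, 77–105 and 105–133.
- With a first session on Day 1 to Day 7, the first reading comes between 21 − 7 = 14 and 49 − 1 = 48 days into treatment.

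**End of treatment**

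Section 8.6 starts Week 1 at the first session or on Day 7, whichever is earlier, and allows two further weeks for make-up visits. With Week 1 starting on Day s:

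- Last scheduled day = s + 112 − 1, which is Day 112 (s = 1) to Day 118 (s = 7).
- Last make-up day = that + 14, which is Day 126 to Day 132.

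| Fourth call | Scheduled days after it | With make-up visits |
|---|---|---|
| Day 105 (earliest) | 7–13 | 21–27 |
| Day 112 (target) | 0–6 | 14–20 |
| Day 133 (latest) | 0 | 0 |

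**The case against.** A reader might infer that the end of treatment goes unobserved. The documents do not support that. The fourth call is targeted at week 16, so a closing reading is planned by telephone, and the 27-day figure needs a Day 7 start, the earliest permitted call and both make-up weeks. Other surveillance continues throughout. Therapists monitor symptoms at each session (11.1.4). Table 3 requires action on dizziness, breathlessness, chest pain and acute pain, and a report of every fall. Participants are told to report adverse events at any time (11.3). What can be missing is one structured reading, not all knowledge of the events. This stands, and it makes the end gap a secondary point.

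A reader might also argue that the last weeks matter most because training load peaks then. The protocol does not prescribe that. The heart-rate target is constant from week 3 to week 16, and strength work stays at three sets at the eight-repetition maximum from the third session on (8.3). Absolute load may progress, but the prescribed relative intensity does not.

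Nor do the documents show that pre-existing and new symptoms can never be separated. The wording and recall period of the form and the content of the Baseline Interview are not given. Either might ask about new or worse symptoms, or cover them by site. Table 1 also lets the first session slip by up to 16 weeks, so a late starter could be called before treatment. These points rule out an absolute claim. They do not supply a planned pre-intervention reading.

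Finally, 12.2.2 counts events attributable to the underlying condition as expected, so a simple tally may be all that is intended. That is a fair description of the form. It does not help the DSMB judge whether a rate is disproportionate, because neither 12.3 nor 12.8 attaches a rate to the listed symptoms.

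**Conclusion.** The point holds as a gap in interpretability. The Expected AE Form is planned only for the calls, and the documents describe no site-specific reading before the intervention. Its counts therefore cannot reliably be read as treatment-emergent. The other baseline information covers this only in part.

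The timing gap is smaller: 0–6 scheduled days for an on-target call, 14–20 with make-up visits, and 27 at most. These figures assume that the fourth call is made within its window and that sessions follow the limits in 8.6.

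How many reports would reflect symptoms present at entry cannot be computed, because the documents give no entry prevalence for them. The conclusion also assumes that neither the form nor the Baseline Interview already captures change from entry. If either does, the main point weakens accordingly. The primary analysis of walking distance is not affected. This is an inexpensive improvement to the safety data and not a defect that threatens the trial.

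**What to change.** Add the existing Expected AE Form to the baseline list in 10.1, given before the first intervention session. Add it to the 16-week list in 10.2, covering the time since the last call. Align 9.6.4, 12.3 and 12.5 with the two added occasions. State in the reporting plan that expected AEs will be shown as new or worse than baseline alongside total reports, for both the final report and the DSMB tables. The telephone schedule need not change.

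Section 6.1 places the follow-up assessment after the intervention is completed, so a form given there closes the end gap when that order is kept.

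The cost is a few minutes per participant at two visits already scheduled, plus a minor amendment. For anyone already past baseline, a starting level could be obtained only by recall, so the change is worth most if made early.
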